# 4.2 Blinding

HYDRATE is a outcome assessor blinded trial, since the intervention is not blindable. The attending anaesthesist can be unblinded during the safety interview before anaesthesia induction. The endpoint assessment will be blinded.

If the safety interview is conducted in a way that unblinds the attenting anaesthesist (e.g. asking the patient if fluids were consumed in the past 2 h) measures must be taken to avoid unblinding the staff responsible for assessing the outcomes (e.g. conducting the safety interview while the staff assessing the outcome is not present in the room). If unblinding occurs the remaining visits should be conducted by blinded staff whenever feasable.

Unblinding of the staff conducting outcome assessment will be documented in the eCRF for visit 4-6 respectivly.

# 5 METHODS: DATA COLLECTION, MANAGEMENT, ANALYSIS

## 5.1 Data collection Methods

## 5.1.1 Case Report Form (CRF)

Data will be entered into an eCRF designed in REDCap by the Investigator or an authorised member of the study team.

## 5.2 Retention

As follow up ends before hospital-discharge, we do not expect relevant issues with retention.

# **5.3 Data Management**

The information entered into the eCRF is systematically checked for completeness, consistency and plausibility by rules implemented in the EDC Tool such that discrepancies can be dealt with at data entry.

## 5.3.1 Archiving

All relevant trial documentation (Trial Master File) and the electronically stored data will be stored for at least 15 years by the sponsor after the trial's completion. At the trial sites, the investigators' files, patient identification lists, signed written consent forms, electronic copies of all eCRFs and the patients' files will be stored for at least 15 years after the trial's completion. If local rules or other legal requirements require longer periods of archiving, then these are to be met especially for the local patient files.

# 5.4 Endpoints

Endpoints are assessed as described in chapter 3.6.3-3.6.5

The primary efficacy outcome is thirst on an ordinary scale from 1 to 3.

With the assessment of this patient relevant endpoint prior to anaesthesia we keep the Statistical Description of the trial hypothesis.

## 5.4.1 Statistical Hypotheses/Statistical Estimation Method

H0: Clear fluid intake until call to the operating room is not associated with reduced thirst at anaesthesia induction compared to restriction of clear fluid intake within 2 hours prior to anaesthesia induction on the Bauer satsifaction questionnaire item #3.

The primary endpoint will be analysed by chi-square test.

# 5.5 Sample Size

We plan randomising n=174 patients. n = 174 (55 per group +5% Dropout)

The primary endpoint of this study is thirst immediately before anaesthesia induction. For this purpose, the Bauer Satisfaction Questionnaire is dichotomised - "yes (moderate or strong)" vs. "no thirst". The three groups will be compared with each other. In the control group, based on Bauer et al, 2001, a value of 53% is assumed based on our own experience it is assumed that the experimental intervention (group 3) has a relative effect of 50% and therefore only 26.5% of patients are still thirsty. For group 2 (Instructed guideline adherence) a somewhat weaker effect is assumed. We assume that thirst can be reduced to 30% in this group.

In order to detect these differences between all three groups using a Chi² test with a power of 80%, a total of 165 patients is needed - 55 patients per group.

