# 2.2 Choice of Comparators

## 2.2.1 Hypothesis

We hypothesize that - compared to standard practice - allowing Patients ≥ 18 years of age undergoing surgery under anaesthesia care to drink clear fluids up to a volume of 200 ml between 2 h prior to anaesthesia and the call to operation room (approximately 30 min prior to anaesthesia induction) will decrease patient thirst and increase patient satisfaction.

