# 2.3 Study objectives

## 2.3.1 Primary Objective

To evaluate if allowing patients to drink clear fluids until call to the operating room prior to anaesthesia induction will improve patient thirst compared to allowing clear fluid intake up to 2 h prior to anaesthesia induction.

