## 3.2 Interventions

Group 1 (control) - Usual care: Fasting instructions as given by anaesthesiologist according to national guidelines (6 h solid meal and thick liquids, 2 h clear fluids).

Group 2 (intervention) - Instructed guideline adherence: As per "Usual care". In addition, the patients will be visited to support and encourage them in drinking clear fluids freely until 2 h before the anticipated anaesthesia induction.

Group 3 (intervention) - Experimental intervention: As per "instructed guideline adherence" with the difference that patients are educated and encouraged to drink up to 200 ml clear fluids between 2 h prior to anaesthesia induction and the call to operation room. Education and information dissemination measures will be taken. Patients receive a container of known volume (e.g. cups, glasses, mugs, bottles with volume marks). From this concludes that patients are allowed to drink up to 100 ml clear fluids every 1 h anaesthesia induction is postponed. Patients may vary their fluid intake to meet this stipulation and their personal needs

e.g. by drinking 100 ml every hour or any other way that does not surpass 200 ml per 2 h (see Fig. 1).

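### The primary comparison is not named: H0 sets Group 3 against a 2 h limit that two arms share, and the stated 80% power does not cover all the group comparisons announced in 5.5

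*Combined protocol and SAP*

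**What the plan says.** - **Null hypothesis (5.4.1).** Drinking until the call is not associated with less thirst "compared to restriction of clear fluid intake within 2 hours prior to anaesthesia induction". The only analysis statement is "The primary endpoint will be analysed by chi-square test".
- **Primary objective (2.3.1).** Whether drinking until the call "will improve patient thirst compared to allowing clear fluid intake up to 2 h prior to anaesthesia induction".
- **Hypothesis (2.2.1).** The reference is worded differently: "We hypothesize that - compared to standard practice - allowing Patients" to drink up to the call will reduce thirst.
- **Arms (3.2).** Group 1 is usual care, with a 2 h clear-fluid limit under national guidelines. Group 2 has the same limit, with visits to "support and encourage them in drinking clear fluids freely until 2 h before the anticipated anaesthesia induction". Group 3 has the Group 2 measures plus drinking between 2 h before induction and the call.
- **Sample size (5.5).** The endpoint is dichotomised (any thirst v none), with assumed rates of 53%, 30% and 26.5% in Groups 1, 2 and 3. The section states "The three groups will be compared with each other". It gives 55 per group for 80% power "In order to detect these differences between all three groups" by a chi-square test.
- **Synopsis, Biometry.** One treatment effect is promised as an odds ratio, with rate difference and relative risk as secondary measures. No pair of groups is named. The trial overall is said to have 80% power at alpha 0.05.

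No section gives an order of testing or an adjustment for the pairwise comparisons.

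**The concern.** The hypothesis needs one comparator and the plan offers at least four readings: a three-group test, Group 3 v Group 1, Group 3 v Group 2, or Group 3 v both 2 h arms pooled. They answer different questions and differ greatly in power.

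Two wrong conclusions become possible. First, Groups 2 and 3 share the encouragement visits. A significant three-group result could come entirely from those visits, yet be reported as rejecting a null hypothesis about drinking until the call. Second, Group 3 v Group 2 is the only pair that isolates late drinking. A non-significant result there would say little, but 5.5 makes it look covered by the 80%.

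**Working it through.** **Inputs.** Rates p1 = 0.53, p2 = 0.30, p3 = 0.265 and n = 55 per group (5.5); alpha 0.05 (synopsis), taken as two-sided because a chi-square test is non-directional and the synopsis gives two-sided intervals.

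**Step 1: reproduce the plan's figure.** For a three-group chi-square with 2 df, the non-centrality is n × Σ(p − p̄)² / [p̄(1 − p̄)].

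- p̄ = (0.53 + 0.30 + 0.265)/3 = 0.365
- Σ(p − p̄)² = 0.165² + 0.065² + 0.100² = 0.04145
- Non-centrality = 55 × 0.04145 / (0.365 × 0.635) = 9.84, which gives power 80.9%
- At n = 54 power is 80.1%, and at n = 53 it is 79.3%, so 54 per group are needed

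The planned 55 fits this test. It also fits Group 3 v Group 1 alone, which needs 53 per group. The sample size therefore cannot show which test was meant. The inflation to 58 for 5% drop-out is also right: 55/0.95 = 57.9.

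**Step 2: power for each pair.** Power ≈ Φ[(|d| − 1.96 × SE0)/SE1], with SE0 from the pooled rate and SE1 from the separate rates.

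- Group 3 v 1: d = 0.265, SE0 = 0.0933, SE1 = 0.0898. Φ(0.91) = 82.0%.
- Group 2 v 1: d = 0.23, SE0 = 0.0940, SE1 = 0.0914. Φ(0.50) = 69.2%.
- Group 3 v 2: d = 0.035, SE0 = 0.0859, SE1 = 0.0858. Φ(−1.55) = 6.0% in the right direction, plus 0.9% in the wrong direction, total 6.9%.
- Group 3 v Groups 1 and 2 pooled (26.5% of 55 v 41.5% of 110): d = 0.15, SE0 = 0.0795, SE1 = 0.0758. Φ(−0.08) = 46.9%; simulation gives 47.3%.

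Exact binomial enumeration gives 82.2%, 69.0% and 6.9% for the three pairs.

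| Comparison | Power at 55 per group | n per group for 80% |
|---|---|---|
| Three-group test | 81% | 54 |
| Group 3 v 1 | 82% | 53 |
| Group 2 v 1 | 69% | 71 |
| Group 3 v 1+2 pooled | 47% | not needed here |
| Group 3 v 2 | 7% | about 2,600 |

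In simulation at the plan's rates, all three pairwise tests are significant together in 2% of trials.

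**Step 3: suppose late drinking adds nothing.** Set Groups 2 and 3 both to 0.30.

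- p̄ = 0.3767 and Σ(p − p̄)² = 0.1533² + 2 × 0.0767² = 0.0353
- Non-centrality = 55 × 0.0353 / (0.3767 × 0.6233) ≈ 8.3, and the three-group test rejects 73% of the time
- Group 3 v 1 rejects 69% of the time (the same rates as Group 2 v 1 above)

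**Step 4: error rate of the pairwise tests.** With equal rates in all arms (tried at 53%, 36.5%, 30% and 26.5%), three unadjusted tests have a family-wise error of 11% to 13%. If they are run only after a significant three-group test, it is 5.0% to 5.2%. Under that gate, power at the plan's rates falls to 76% (3 v 1), 66% (2 v 1) and 7% (3 v 2).

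**The case against.** The strongest reply is that 5.5 describes one chi-square test and one total of 165, so the 80% belongs to a three-group test, for which it is correct. Group 1 is also the only arm labelled control, 2.2.1 refers to standard practice, and 5.5 sets the Group 3 effect against the control rate. On that view the comparator is Group 1, and pooling Groups 1 and 2 is proposed nowhere.

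Much of this stands. There is no arithmetic error in the sample size, the 47% belongs to a reading the wording permits but does not propose, and the 11% to 13% error applies only if the pairwise tests are ungated. But the two halves of the reply point to different primary tests. A non-directional three-group test does not establish the Group 3 effect in H0, while Group 3 v Group 1 is designated nowhere. The wording of 2.3.1 and 5.4.1 fits Group 2 equally well, and 4.1 describes only two groups at 1:1, which does not help.

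It is also fair that Group 3 v Group 1 does not isolate late drinking, since it rejects 69% of the time in Step 3. That limits what the primary result can claim and has to be stated. An interval for Group 3 v 2 still excludes large differences, which has value in a pilot. The pilot label does not settle the matter, because the synopsis claims 80% power at alpha 0.05.

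**Conclusion.** The concern holds and should be corrected before any comparison of the arms. The plan does not identify its primary contrast. The 80% is true for the three-group test (81%) and for a single unadjusted Group 3 v Group 1 test (82%). It is not true for Group 2 v 1 (69%), for Group 3 v the pooled 2 h arms (47%) or for Group 3 v 2 (7%).

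These figures rest on the plan's assumed rates, 55 evaluable patients per group, the dichotomised endpoint and a two-sided 0.05 level without continuity correction. That 5.5 intends a three-group test is an inference from the sample size, not something the plan states.

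**What to change.** 1. In 5.4.1, 5.5 and Biometry, name one primary contrast: Group 3 v Group 1, a 2x2 chi-square on the dichotomy already in 5.5, two-sided 0.05, not conditional on a three-group test. State the dichotomy in 5.4.1 as well.
2. In 2.3.1 and H0, name usual care (Group 1) as the comparator, in line with 2.2.1.
3. State that this contrast estimates the whole Group 3 package, encouragement plus late drinking.
4. For the other two comparisons, either label both exploratory, or test Group 2 v 1 and then Group 3 v 2 at 0.05, each only if the previous test is significant. With the fixed order, give the power to reach significance as about 82%, 62% and 2% along the sequence (82%, 69% and 7% for each test alone).
5. Report Group 3 v 2 as a rate difference with its 95% interval. The expected half-width is 1.96 × √(0.30 × 0.70/55 + 0.265 × 0.735/55) = 0.168, about 17 points.
6. Limit the 80% statement to the primary contrast, and name the pair for the odds ratio, rate difference and relative risk.

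**Cost.** Only protocol wording changes, with no extra patients and no split of alpha. Because the primary objective is reworded, the sponsor should check whether 7.3 requires ethics committee re-appraisal. The power stated for the other comparisons becomes less favourable, and the primary conclusion covers the package, not late drinking alone.

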#### Drop-outs

Assuming 5% drop-outs or non-informative patients we require 58 patients per group.

#### 5.6 Statistical Methods

## 5.6.1 Analysis Population

The Full Analysis Set (FAS) will be as close as possible to the ideal implied by the intention-to-treat-principle.

## 5.6.2 Planned Methods for Analysis

Standard methods of descriptive statistics (e.g. chi-square test for the primary endpoint) will be used always indicating the number of valid and missing values. Summary statistic will be reasonably rounded to avoid pseudo-precision.

Demographic and other baseline parameters will be described for the whole FAS and by randomisation arm using standard methods appropriate to the scale.

Patients will be listed on whom no intervention or an intervention not corresponding to the randomisation arm was performed.

# 6 METHODS: HARMS/ ADVERSE EVENTS (AE/SAE)

The focus of this clinical trial is to find an appropriate fluid fasting strategy to optimize the risk-benefit ratio. HYDRATE investigates different fasting strategies concerning patient thirst.

Immediate safety of drinking fluid is not in the primary focus of the trial and generally considered safe.

Therefore, the collection, documentation and notification of safety relevant events are adapted for this clinical trial. Following data are of special interest:

• Data defined as **end points** (primary, secondary and safety).

## 6.1 Definition of (serious) adverse events

## 6.1.1 Adverse Events (AE)

Adverse events encompass any unfavorable and unintended sign (including an abnormal laboratory finding, for example), symptom, or disease that arise newly or worsen after the beginning of the intervention.

## 6.1.2 Serious Adverse Events

An adverse event is defined to be serious if it

- results in death.
- is life-threatening,
- requires in-patient hospitalization or prolongation of existing hospitalization,
- results in persistent or significant disability/incapacity

Note: The term "life-threatening" in the definition of "serious" refers to an event in which the patient was at risk of death at the time of the event; it does not refer to an event which hypothetically might have caused death had it been more severe.

Medical and scientific judgement should be exercised in deciding whether expedited reporting is appropriate in other situations, such as important medical events that may not be immediately life-threatening or result in death or hospitalisation but may jeopardise the patient or may require intervention to prevent one of the other outcomes listed in the definition above. These should also usually be considered serious.

# 6.2 Documentation of (serious) adverse events

Within this trial all variables defined as safety outcomes **meeting the definition of AE/SAE** will have to be reported to the Investigator in writing as soon as possible and documented on the eCRF. The eCRF has to be filled in shortly after each study visit.

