## Safety Endpoints:

- 10. Unplanned postoperative admission to an intermediate care unit (IMC) or intensive care unit (ICU) due to respiratory insufficiency.
- 11. Confirmed Bronchopulmonary aspiration
- 12. Death within observation period

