## 3.6.4 Visit 4: Assessments immediately after anaesthesia induction

- If relevant bronchopulmonary aspiration is suspected, it needs to be confirmed by bronchoscopy or radiology imaging up to 48 h after anaesthesia procedure. In that case the patient will be monitored for an additional 48 h and the outcome will be documented in the eCRF and the AE/SAE section if applicable. The sponsor is to be informed of every instance of confirmed bronchopulmonary aspiration within 24 h even if the SAE criteria are not met. The risk/benefit consideration has to be revaluated.
- Vital signs including heart rate and blood pressure will be collected from the routine data. The lowest value 15 min after anaesthesia induction will be documented.
- If not already done, a blood sample for glucose levels is to be drawn.

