# **6.3** Other Safety Relevant Issues

Other safety issues also qualify for expedited reporting where they might substantially alter the current benefit-risk assessment of an investigational intervention or would be sufficient to consider changes in the investigational intervention or in the overall conduct of the trial, for instance:

New events related to the conduct of a trial likely to affect the safety of subjects, such as:

- a serious adverse event which could be associated with the trial procedures, and which could modify the conduct of the trial,
- a significant hazard to the subject population such as lack of efficacy of intervention,
- a major safety finding from a newly completed preclinical study.
- a temporary halt of a trial for safety reasons if the trial is conducted with the same investigational intervention in another country by the same sponsor.

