## 10.1.4 Expected/Unexpected

Adverse Events are unexpected if they are no safety outcomes or regurgitation.

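### Section 6.2 routinely documents only the three safety outcomes, so other non-fatal SAEs depend on ad hoc recognition, and regurgitation is classed but not collected

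*Combined protocol and SAP*

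**What the plan says.** The reporting rule is in section 6.2: "Within this trial all variables defined as safety outcomes" that meet the AE/SAE definition "will have to be reported to the Investigator in writing as soon as possible and documented on the eCRF".

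The safety endpoints in section 3.5.2 are:

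- "Unplanned postoperative admission to an intermediate care unit (IMC) or intensive care unit (ICU) due to respiratory insufficiency"
- "Confirmed Bronchopulmonary aspiration"
- "Death within observation period"

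Four other places bear on the same events:

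- Section 10.1.4 sorts events by expectedness: "Adverse Events are unexpected if they are no safety outcomes or regurgitation".
- Section 6.3 makes further safety issues eligible for expedited reporting. One example is "a serious adverse event which could be associated with the trial procedures, and which could modify the conduct of the trial".
- Section 3.6.4 adds a deadline for one event: "The sponsor is to be informed of every instance of confirmed bronchopulmonary aspiration within 24 h even if the SAE criteria are not met". It also calls for the risk/benefit assessment to be revisited.
- The opening of section 6 says that safety collection has been adapted because drinking is regarded as generally safe. It names the primary, secondary and safety end points as the data of special interest.

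**The concern.** The definitions in 6.1.1 and 6.1.2 are broad, while the documentation duty in 6.2 is narrow. Two other parts of the plan use events outside that duty: 10.1.4 classifies them, and 6.3 may expedite them. No routine step is described that brings such events to the investigator's attention in the same way in all three arms.

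Ad hoc recognition matters here because patients and the attending anaesthesiologist may know the allocation. Whether an event gets written down could then depend on whether somebody already suspects the drinking regimen. A between-arm table of SAEs built this way would be hard to interpret.

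Regurgitation is a separate gap. Section 2.1 names it, together with aspiration, as what fasting rules exist to prevent. If it occurs at induction without confirmed aspiration, the plan gives it a label but no place to be recorded.

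**Working it through.** There is no stated figure to reproduce. The check sets the passages side by side.

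**Step 1. SAE criteria (6.1.2) against the routine duty (6.2 with the safety endpoints in 3.5.2).**

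| SAE criterion | Inside the routine duty? |
|---|---|
| Death | Yes, any cause within the observation period |
| Life-threatening | Only if it is also a respiratory IMC/ICU admission or confirmed aspiration |
| Hospitalisation or its prolongation | Same restriction |
| Persistent or significant disability | Same restriction |

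One of the four criteria is wholly covered. A cardiac event leading to ICU admission is an example of a non-fatal SAE outside the duty.

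**Step 2. Expectedness (10.1.4) against 6.2.** I read 10.1.4 as neither/nor: an event is unexpected if it is neither a safety outcome nor regurgitation. Events within 6.2 are safety outcomes, so they are expected under that rule. Unexpected events lie outside 6.2. There is one bridge: 10.1.5 says a death is the consequence of an event, and that event must be fully documented. If the underlying event is not itself a safety outcome or regurgitation, it is unexpected and still recorded.

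**Step 3. Other routes for non-fatal SAEs.**

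- 6.1.2 leaves expedited reporting of other important medical events to medical and scientific judgement.
- 6.3 qualifies an SAE possibly linked to trial procedures for expedited reporting. It says what qualifies, but does not tell staff to look for or record every SAE.
- 6.4 requires treatment of any AE/SAE to be documented, but allows this in documents outside the CRF.
- 3.6.4 mentions an AE/SAE part of the eCRF. Its content is not shown.

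These routes exist, but none is a routine, uniform collection step that would support a table by arm.

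**Step 4. Regurgitation.**

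- Endpoints (3.5.2): absent.
- Schedule (1.2.1): no row. The aspiration row is marked at V4 and V5.
- Visit 4 (3.6.4): suspected and confirmed aspiration only.
- Visit 5 (3.6.5): PONV up to 2 h, including vomiting and retching. This is postoperative and does not capture regurgitation at induction.
- Appendix (10.1.4): named as a category.

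**Step 5. Recipient and timing.** Section 6.2 sends reports to the investigator as soon as possible. Section 3.6.4 sends confirmed aspiration to the sponsor within 24 h, whether or not SAE criteria are met. That wording presupposes an SAE route to the sponsor, but section 6 states neither that route nor a deadline.

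**Step 6. Context for the aspiration endpoint.** Assume all 58 randomised patients in Group 3 are assessed and none has confirmed aspiration. The two-sided 95% upper limit is then 1 − 0.025^(1/58) = 0.0616, or 6.16%. This limit comes from the sample size, and no reporting rule changes it. It shows only that the confirmed-aspiration count alone will say little about safety.

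**The case against.** The best defence is that the narrowing is deliberate. Section 6 says safety is not the primary focus and that collection is adapted. In a single-centre pilot of 174 patients, followed until about 2 h after the procedure, a sponsor may reasonably choose a short list. Many untoward events are also collected as secondary outcomes: delirium, headache, vasopressor dose, vital signs and PONV. The word only does not appear in 6.2, and an eCRF field for other SAEs may exist. The investigator/sponsor contrast may be slight if the roles overlap at one centre. No passage attaches a consequence to the label unexpected.

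Much of this stands, and it rules out three stronger readings that a reader might infer:

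- **That other SAEs can never be captured.** The documents do not support this. Sections 6.1.2, 6.3 and 6.4 give ad hoc routes, and all deaths are safety outcomes.
- **That the expedited-reporting clause in 6.3 has nothing to act on.** It can act on serious aspiration, on death, and on any SAE that somebody links to trial procedures.
- **That every recorded event is expected by definition.** Section 10.1.5 brings in the event behind a death, which may be unexpected under 10.1.4.

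The defence does not explain why 10.1.4 and 6.3 rely on events for which 6.2 sets no duty, or why regurgitation is classified without being collected. A declared adaptation should still be internally consistent, and a form that is not described does not replace a written duty.

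**Conclusion.** The point holds as a gap in routine collection. Followed as written, the plan systematically records three safety outcomes. Other non-fatal SAEs depend on individual recognition. Unexpected events have no routine collection step except where a death is traced to its cause. Regurgitation is classified but collected nowhere.

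The consequence is limited. The primary thirst comparison is untouched, and confirmed aspiration and death are covered. The number of events that would go unrecorded cannot be estimated, because the documents give no rate for other SAEs or for regurgitation in this population. This is a worthwhile, inexpensive improvement to the safety data and does not threaten the trial's validity.

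The conclusion rests on three assumptions:

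- Section 6.2, read with the opening of section 6, is meant as the full routine duty.
- Section 10.1.4 is meant as neither/nor. If regurgitation were instead meant to be unexpected, it would still be uncollected.
- The eCRF has no undescribed fields that already close the gap.

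**What to change.** 1. **Section 6.2.** State that all SAEs from the start of the intervention to the end of the last visit are documented in the eCRF, whether or not they are safety outcomes, and tabulated by arm. Define that start: the synopsis places the intervention on the day of surgery, whereas section 3.6 runs it from randomisation, and visit 1 can fall up to 28 days before surgery.
2. **Recipient and timing.** Reconcile 6.2 with the 24 h sponsor notice in 3.6.4, so that one rule says who is told of an SAE and by when.
3. **Visits 4 and 5.** Extend the existing aspiration row to record regurgitation, suspected aspiration and confirmed aspiration separately. Tabulate the counts by arm, descriptively and without a test.
4. **Section 10.1.4.** Reconcile it with 6.2, so that each category named there has a collection step and the neither/nor wording is unambiguous.

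The cost is protocol wording, a small extension of one eCRF item at two visits, and a few extra SAE forms for events due to the surgery itself. With 174 patients and short follow-up, that burden is small. If the sponsor prefers to keep the narrow scope, the minimum is to say so in 6.2, give the reason, and remove or adapt the parts of 10.1.4 and 6.3 that rely on events not routinely collected.
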